5. Have evidence of clinically significant organic disorder on the history and/or physical examination that would, in the opinion of the Investigator, put the patient at risk, prevent the patient from completing the study, or otherwise affect the outcome of the study.
6. Have a history of genital herpes because of the episodic nature of genital herpes and of the known possibility of occurrence of herpetic pain without visible dermatologic manifestations of herpes. Genital herpes and its accompanying genital pain may obscure the source of the genital pain experienced and confound the ability to determine the efficacy of treatment/placebo on endpoint of alleviation of pain in women with SPVD.
7. Have any infection of the genitalia
8. Have lichen sclerosis, lichen planus, contact dermatitis, psoriasis or any inflammatory condition or abrasions of the vulva
9. Have an episiotomy scar in the area where pain is perceived as it may confound the etiology of the perceived pain
10. Have diabetes.

5. STUDY PROCEDURES:

Duration of Study:

Once subjects are screened and enrolled into the study, the duration of participation in the study will be 4 weeks from the beginning of the study to the last visit. Follow up questionnaires will be filled out at 6 weeks and electronically entered or mailed in to your clinical trial gynecologist's study clinic office.

Subjects will be given a written description of the study and possible untoward effects of the protocol. They will sign the IRB-approved informed consent. The schedule and activities of visits will be given to the subject, along with instructions about notification in case of untoward events.

Accepted subjects will be randomized and only a non-participant in the clinical trial will hold the code. Except for subjects who decide to leave the trial because of any adverse reactions (i.e.. irritation), prior to its completion, the code will not be broken prior to the completion of the last subject's protocol.

Study Procedures:

Each and every procedure performed is a standard procedure. These procedures will be performed at a screening visit and each of the three subsequent study clinic visits. Initial screening; week 0, week 2; week 4 . Please note, in addition to study related procedures that a standard of care medical history, including past and current medical history, medications, allergies, height, weight and blood pressure will be taken initially and reviewed for any changes on each study clinic visit.

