- Apply the ointment once a day; if any irritation occurs stop using the ointment and notify your clinical trial gynecologist Do not restart to use the ointment until your irritation completely resolves. You will then be instructed to reduce the frequency of application to twice per week or less depending on your discussion with and instructions from your clinical trial gynecologist .
- Do not wash off the ointment from the treated area before the next application. When you wash the treatment area or bathe, apply the ointment afterwards, not before.
- Treatment with the ointment should be continued for a total of 4 weeks as instructed by your clinical trial gynecologist.. You will be seen at regular intervals during this time period by your clinical trial gynecologist.

•The ointment is not a cure for any condition and your condition may reoccur during or after treatment and may need further treatment.

What should I avoid while using catechins ointment?

- Do not apply the ointment on open wounds.
- While being treated with the ointment, and you do choose to have sexual contact, (genital, anal or oral) note that the ointment may weaken condoms and vaginal diaphragms therefore you must wash off the ointment carefully before having protected sexual contact. Talk to your doctor about safe sex practices.
- Avoid contact with your eyes, nostrils and mouth while ointment is on your finger(s).
- Do not expose the genital area treated with the ointment to sunlight, sunlamps or tanning beds.
- Do not cover the treated area. Loose-fitting undergarments can be worn after the ointment

PLEASE NOTE• The ointment is naturally a light reddish-tan color and therefore may stain your light-colored clothes and bedding. It is recommended to wear darker colored undergarments or an unscented disposable cotton panty liner while using the ointment.

How should I store catechins ointment?

- Store the ointment refrigerated or up to 77°F (25°C). • Do not freeze the ointment.
- Make sure the cap on the tube is tightly closed.
- Bring the tube of the ointment when you come to your scheduled clinic study visits.

Keep all medicines out of the reach of children. Do not give the ointment to other people, even if they have the same symptoms.

All subsequent visit dates for the treatment period will be calculated from Week 0 (Visit 1) date.

Week 2 (Visit 2)

The following procedures will be performed at the study clinic at the end of Week 2:

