Distribution of new copies of the SAL, FSFI, NRS, VVSQ, FSDQ-R, a question about any change in medications, along with self-addressed envelopes which will be labeled with the patient number for their return to the Investigator. Instructions will be given to complete the questionnaires at the conclusion of week 6 .

Alternatively, subject will be filling out questionnaires on secure, HIPAA compliant, website.

Consent Protocol:

Subjects will be given a written description of the study and possible untoward effects of the protocol. They will sign the IRB-approved informed consent.

Accepted subjects will be randomized and only a non-participant in the clinical trial will hold the code. Except for subjects who are excused from the trial prior to its completion because of any adverse reaction (i.e. irritation) the code will not be broken prior to the completion of the last subject's protocol.

Subjects will be consented at the initial study visit by the clinical trial gynecologist.. The clinical trial gynecologist will be available for consent discussion.

The Study Treatment: Drugs – The 10% GTO (10% 7.5% sinecatechins ointment, diluted Veregen ®) in petrolatum ointment will be furnished by Town Total Compounding Center Pharmacy ([name]), at week 0, in numbered, but otherwise unmarked compressible opaque, 15 gram tubes that will be examined at each visit. The placebo will be petrolatum ointment with an inert vegetable dye to visually appear the same as the drug. Subjects will be instructed to bring in their tubes at their 2 and 4 -week visits. The subjects will be instructed in the application of one ½ inch strand of either the study drug: 10% (diluted Veregen) or placebo once daily to the vulvar vestibule. Application – Subjects will be instructed to apply a ½ inch strand, lightly to painful or reddened areas of the vulvar vestibule. This is done daily for four weeks. Subjects will apply with a fingertip, taking care to avoid placing it into the vagina. (detailed instructions provided in this document) .

Compliance: At each visit the tubes will be weighed.

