6. Risks/Safety Information- The risks of full strength topical Veregen® (15% sinecatechins ointment) are well known and well documented in the accompanying package insert. Veregen® Medigene, (Green Tea ointment, (GTO), 15% sinecatechins) is a topical FDA approved drug (2006) indicated for the treatment of external genital warts, since 2006. The package insert specifies it to be applied to each and every visible wart three times a day. The safety profile for Veregen® has been well established. The application of one ½ inch strand of 10% (diluted Veregen) once daily to the vulvar vestibule does not cause the potential irritation that multiple 0.5cm strands of 15% (full strength Veregen) can cause.

The use of significantly lesser doses of the drug (one ½ inch strand), once a day vs the use of multiple 0.5cm strands three times a day and use of a lower concentration of the study drug 10% sinecatechins will significantly reduce the risk of adverse reactions to the drug as seen in the on-label use of the marketed drug Veregen® 15% sinecatechins. In fact, the use of 10% sinecatechins, ½ inch strand, topically applied, once daily to the vulvar vestibule was found to be soothing, and reduced or eliminated vulvar pain in post-menopausal women with secondary provoked vestibulodynia (SPVD).

In Phase 3 clinical trials, a total of 397 subjects received Veregen® (15% sinecatechins) three times per day topical application for the treatment of external genital and perianal warts for up to 16 weeks.

Local irritation is the main potential side effect and in fact the goal of treatment of external genital warts with full strength Veregen (15% sinecatechins ointment) by simultaneously applying a 0.5cm strand to each and every one of multiple visible genital warts three times daily for up to 16 weeks. The mechanism of action of Veregen in clearing genital warts is unknown. (see package insert for Veregen). It was discovered that the off-labeled use of diluted Veregen (10% sinecatechins ointment) applied as a single ½ inch strand once daily was safe and effective in alleviating the pain from SPVD, as demonstrated in the off-labeled use of Veregen with patients in private practice as also seen with 5% sinecatechins ointment (see US Patent 9750716). The mechanism of action of Veregen for treating secondary provoked vestibulodynia (SPVD) is unknown but may be due to Veregen's (sinecatechins, green tea extract) known action as an antioxidant/anti-inflammatory.

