The study medication and placebo have a red brown color and may therefore stain underwear. Subjects will be advised to wear panty liners every day that they apply the study medication in order to avoid staining of their underwear with the medication or placebo.

7. Monitoring and Reporting of Adverse Events/Serious Adverse Events: During the study, if you experience any medical problems, suffer a research-related injury, or have questions, concerns or complaints about the study, please contact your clinical trial gynecologist. If you seek emergency care, or hospitalization is required, alert the treating physician that you are participating in a research study being conducted by your clinical trial gynecologist.

Monitoring of Adverse Events will be done by patients reporting any adverse event to their clinical trial gynecologist. No serious adverse events are expected.

8. Study Oversight: In the unlikely event of the need to prematurely terminate this study of 10% , [name] will be the one to decide to terminate the study. The study will be made available for monitoring, auditing, IRB review and regulatory inspection by providing direct access to study related source data.

9. Data Management- Preliminary Power Analyses and Sample Size Estimates

Power Analyses

For Primary Outcome: Pain Score:

Sample size was calculated to achieve at least 80% power with a significance level of 0.05 using a two-tailed, two-sample t test. A sample size of 56 subjects (28 subjects in treatment group and 28 subjects in the placebo group) was estimated to achieve 80% power to detect at least 2.0-points mean difference between treatment and placebo groups. The Initiative on Methods, Measurement, and Pain Assessment in Clinical Trials suggests that reductions in pain intensity of at least 15–20%, or 2 points in the 0–10 scale, reflect clinically important changes (Dvorkin et al, Core Outcome Measures for Chronic Pain Clinical Trials:

IMMPACT Recommendations Pain: 2005 Jan; 113 (1-2) pp: 9-19)). The pain classification on a 0-10 scale will be as follows: 0 no pain; 1-3 mild pain; 4-6 moderate pain; 7-9 significant pain; 10 severe pain. To compensate for possible withdrawal of 15% of patients in the vulvodynia study, a total sample size of 64 participants (32 in the treatment group, 32 in the placebo group) will be required.

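### Women who leave or are excused for an adverse reaction lose their later Q-tip pain scores, and the plan answers withdrawal only by enrolling 64 instead of 56

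*Combined protocol and SAP*

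**What the plan says.** Section 5 mentions exit for a reaction twice, both times as an exception to the rule that the code stays closed until the last subject finishes. Duration of Study has "Except for subjects who decide to leave the trial because of any adverse reactions"; Consent Protocol has "Except for subjects who are excused from the trial prior to its completion because of any adverse reaction". Both give irritation as the example. Breaking the code is the only consequence stated.

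A separate route covers women who are irritated but stay. The Instruction Sheet in Section 5 tells them to stop, wait until the irritation resolves, and resume at twice a week or less. It adds "You will be seen at regular intervals during this time period by your clinical trial gynecologist", and the visit calendar is fixed: "All subsequent visit dates for the treatment period will be calculated from Week 0 (Visit 1) date".

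Pain is scheduled as a Q-tip NRS at screening and at weeks 0, 2 and 4, and as an NRS at weeks 0, 1, 2, 3, 4 and 6. Under Visit 1, each patient is told to expect emails for online questionnaires at weeks 1, 3 and 6. No early-termination visit is listed.

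Section 9 sizes the trial under "For Primary Outcome: Pain Score", "using a two-tailed, two-sample t test", and raises 56 to 64 for 15% withdrawal. Its Statistical Analyses part lists tests for the questionnaires and erythema, and assessment points at baseline and weeks 2, 4 and 6. It names no test for the pain score, no primary time point, no analysis set and no rule for missing data.

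**The concern.** Irritation and the pain outcome involve the same tissue. A woman who exits because the ointment irritates her may well have a different pain score from one who stays, so the missing score may be related to its own value. A comparison of the women still present would then estimate something other than the difference between the randomised groups. Extra enrolment keeps the confidence interval narrow but leaves any such shift in place.

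The shift favours the drug if worse-off leavers come mainly from the active arm, and works against it if they come mainly from placebo. Opening the code at exit adds a second problem: pain is self-rated, so any score given after the code is opened is no longer blinded.

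**Working it through.** **What is lost, by time of exit**
- Exit before week 2: both post-baseline Q-tip scores (weeks 2 and 4).
- Exit between weeks 2 and 4: the week 4 Q-tip score only; the week 2 score is kept.
- Online NRS at weeks 1, 3 and 6: announced to each patient, with nothing said about women who have left. Neither continuation nor cessation is established.

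**The plan's own figure**
- 56/(1 − 0.15) = 65.9, so 66; 56 × 1.15 = 64.4, so 64. The stated 64 is within two women of the first and matches the second. The arithmetic is not the issue.
- Expected withdrawals from any cause: 0.15 × 64 = 9.6, about 10.

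**SD**
The plan states none. For a two-sided 0.05 t test with 28 per arm, 80% power and a 2.0-point difference, the standardised difference must be 0.762, so SD = 2.0/0.762 = 2.62. This is a back-solved assumption.

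**Bias if only stayers are compared**
Let *a* and *p* be the numbers of differing leavers on active and placebo, out of 32 each, and let D be the number of points by which leavers are worse than stayers. Each arm's stayer mean is too low by (number of leavers × D)/32, so with the same D in both arms

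spurious benefit = (a − p) × D/32.

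The rejection rate under no true effect comes from the noncentral t distribution, with noncentrality = bias/(SD × √(1/n₁ + 1/n₂)).

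**Main illustration**
Assume half of the 10 withdrawals are for irritation, split 3 active and 2 placebo, that other leavers do not differ, and that D is 1 to 4.
- Bias: (3 − 2) × 1/32 = 0.031 to (3 − 2) × 4/32 = 0.125 points, which is 1.6% to 6.25% of the 2.0-point target.
- With 29 and 30 women remaining and bias 0.125: SE = 2.62 × √(1/29 + 1/30) = 0.68 and noncentrality is 0.18. Rejection is 5.0% to 5.4% over the range of D. Removing all 10 withdrawals (27 and 27 remaining) gives 5.0% to 5.3%.

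**What larger values require**

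| Differing leavers, active/placebo | Gap D | Bias (points) | Rejection |
|---|---|---|---|
| 5/5 | equal | 0 | 5.0% |
| 6/4 | 1 to 4 | 0.06 to 0.25 | 5.1% to 6.4% |
| 7/3 | 1 to 4 | 0.13 to 0.50 | 5.3% to 10.5% |
| 5/5 | 4 in one arm, 1 in the other | (20 − 5)/32 = 0.47, either direction | 9.9% |
| 5/0 | 1 to 4 | 0.16 to 0.63 | 5.6% to 14.6% |

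The rows with 10 leavers treat every withdrawal, whatever its cause, as a worse-off leaver. Reversing a split reverses the sign: 4/6 gives 0.06 to 0.25 points against the drug.

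**The case against.** The strongest reply is that most irritated women never exit. The Instruction Sheet has them pause and restart on an unchanged calendar, so exit for irritation is a residual path that appears only inside code-break clauses. That stands, and it keeps the number affected small.

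Four stronger readings are tempting, and the documents do not support them.
- *Leavers have no further assessment.* The week 1, 3 and 6 emails are announced to each patient and nothing cancels them on exit. Only the clinic Q-tip score is clearly lost.
- *The plan excludes leavers from the pain analysis.* No text says so. The t test is named for sample size, and no analysis set or primary time point is given. Omission is an inference from that test and from sizing to keep 56.
- *Exits will fall mainly on the active arm and favour the drug.* Section 6 ties irritation to the marketed product ("Local irritation is the main potential side effect and in fact the goal of treatment of external genital warts with full strength Veregen") and says that the daily 10% strand "does not cause the potential irritation that multiple 0.5cm strands of 15% (full strength Veregen) can cause". No irritation rate is given for either arm, so an imbalance is possible but not shown.
- *All 10 expected withdrawals are women with worse pain.* The 15% covers withdrawal in general, and no share for irritation is stated.

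It may also be said that the consent document, which is not in the public text, could set withdrawal terms. It could, but such terms would not normally supply an analysis set or a missing-data rule.

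**Conclusion.** The point holds as a cheap improvement, with moderate confidence. The plan foresees exit for a reaction, lists no exit visit, is silent on whether leavers keep answering questionnaires, and meets withdrawal with enrolment alone. If observed scores are compared by t test, these women are likely to be absent from the later comparisons.

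No bias has been demonstrated. Its size and direction are unknown and it is probably small: 0.03 to 0.125 points in the main illustration, with the false-positive rate barely above 5%. That rests on an SD of 2.62, a stayers-only analysis, a 3/2 split and a gap of 1 to 4 points, none of which the plan states. Bias approaching half a point or more needs marked imbalance between arms or very different gaps by arm.

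**What to change.** 1. In both Section 5 clauses, state that an adverse reaction ends or reduces ointment use but not participation. Unless she withdraws consent, the woman keeps the week 2 and week 4 visits and the week 1, 3 and 6 questionnaires. The Q-tip test is omitted while the tissue is irritated, but an NRS is still collected. If she declines further visits, a pain score is taken at exit.
2. Keep the code closed for these women until the last subject completes, unless it is needed for medical care. Always score pain before any code break.
3. In Section 9, designate which NRS is primary (the plan collects both Q-tip and diary scores). Analyse it at week 4 in all randomised women by assigned arm, with a baseline-adjusted repeated-measures model using all observed visits.
4. Add one sensitivity analysis that gives every woman missing week 4, in either arm, her baseline score.

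The cost is amendment wording, already scheduled visits for a few women (about 10 withdrawals are expected from all causes) and one extra analysis. Including women off treatment or on reduced treatment may shrink the estimated effect slightly. The rule cannot reach women who refuse follow-up. It also cannot recover women who have already left; the amendment rationale shows that enrolment was under way.

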The study drug is Veregen® (sinecatechins) Ointment, an FDA approved, 2006, marketed botanical drug product for topical use in the treatment of external genital warts. The drug Veregen® is 15% sinecatechins, which is a partially purified fraction of the water-soluble extract of green tea leaves from Camellia sinensis, and is a mixture of catechins and other green tea components. Veregen ® is indicated to be topically applied as multiple 0.5 cm strands (i.e., to each and every visible genital wart) three times a day, continuously, for up to 16 weeks. In contrast, the study will be using Veregen ® ointment diluted, by the certified compounding pharmacy, with USP petrolatum w/w, to a drug concentration of 10% sinecatechins.

This diluted Veregen, 10% sinecatechins ointment, will be topically applied to the external genitalia, (vulvar vestibule) as a single ½ inch strand, once a day, for 4 weeks.

The rationale for using 10% Veregen once daily as a single ½ inch strand for a total of 4 weeks vs 6 weeks is that it was demonstrated in private practice to be both therapeutically efficacious during this time interval and without irritation.

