1. Tubes of “the ointment” will be collected.
2. Update to medical/gynecologic/drug history.
3. Physical examination: An examination, including of the vulva and vagina.
4. Vaginal pH
5. Q-tip Test to establish localization and rating NRS of vulvar, vestibular pain.
6. Vital signs including blood pressure and heart rate (after sitting 5 minutes) and body temperature, height and weight.
7. Assessment of acute life stress relating to any major life change that interferes with sexual function.
8. Status of patient’s sexually functional, both psychologically and physically
9. Establishing that patient is sexually active with self (masturbation) and/ or with partner.
10. Collection of completed SAL’s or verifying that questionnaire filled out on secure website.
11. Distribution of new copies of the SAL or verifying that questionnaire to be filled out on secure website
12. Completion of the other questionnaires: FSFI, NRS, VVSQ, FSDQ-R
13. At the end of Visit 2, site personnel will distribute to the subject, a new 2-week, 15 gram, supply of the investigational drug or the placebo (“the ointment”). The subjects will be instructed on how to apply “the ointment”. The subject will be given written instructions on how to apply the ointment.

Week 4 (Visit 3)

The following procedures will be performed at the study clinic at the end of Week 4:

1. Site personnel will collect all tubes of “the ointment”.
2. Update to medical/gynecologic/drug history.
3. Physical examination: An examination, including of the vulva and vagina.
4. Vaginal Maturation Index
5. Vaginal pH
6. Q-tip Test to establish localization and rating NRS of vulvar, vestibular pain.
7. Vital signs including blood pressure and heart rate (after sitting 5 minutes) and body temperature, height and weight.
8. Assessment of acute life stress relating to any major life change that interferes with sexual function.
9. Status of patient’s sexually functional, both psychologically and physically

10. Establishing that patient is sexually active with self (masturbation) and/ or with partner.
11. Collection of completed SAL's or verifying that questionnaire filled out on secure website.
12. Completion of the other questionnaires: FSFI, NRS, VVSQ, FSDQ-R
13. The tubes of the investigational drug or placebo will be collected at this last clinic visit.

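### Section 7 relies on women reporting adverse events themselves and no scheduled contact asks about irritation, so irritation is likely to be under-counted

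*Combined protocol and SAP*

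**What the plan says.** Section 7 describes adverse event collection in one sentence: "Monitoring of Adverse Events will be done by patients reporting any adverse event to their clinical trial gynecologist". The instruction beside it also leaves the first move to the woman: "if you experience any medical problems, suffer a research-related injury, or have questions, concerns or complaints about the study, please contact your clinical trial gynecologist". The instruction sheet in section 5 does the same for irritation: "if any irritation occurs stop using the ointment and notify your clinical trial gynecologist".

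The week 2 and week 4 lists in section 5 have 13 items each. The nearest to a safety question is "Update to medical/gynecologic/drug history". Both lists also include a vulvar and vaginal examination and the VVSQ. The general procedures text adds a yes/no record of vestibular erythema, with its location drawn, at each visit.

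On irritation itself, section 6 says of the 15% product: "Local irritation is the main potential side effect and in fact the goal of treatment of external genital warts with full strength Veregen". It says of the study regimen that it "does not cause the potential irritation that multiple 0.5cm strands of 15% (full strength Veregen) can cause". The synopsis justifies the regimen by private-practice experience that it was "therapeutically efficacious during this time interval and without irritation". Section 5 (Duration of Study and Consent Protocol) gives irritation as its example of an adverse reaction that leads a woman to leave the trial and her code to be broken.

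The Statistical Analyses part of section 9 lists tests for the questionnaires and for erythema. It lists none for adverse events.

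**The concern.** Passive reporting usually finds fewer events than a standard question, especially for mild or short-lived local symptoms. Here irritation is the one reaction the plan foresees and attaches consequences to: the woman stops, may resume less often, and may leave the trial with her code broken. Such an event should be sought in the same way from every woman in both arms.

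The protocol already states that the study regimen avoids the irritation of full strength, and section 12 foresees a publication. A low count from unsolicited reports could be read as confirming that statement when the method had little power to contradict it. Events not recorded at the time cannot be reliably recovered later.

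**Working it through.** **Step 1: what each contact collects, from the visit lists, the schedule table and the week 6 instructions in section 5.**

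| Contact | Items bearing on local reactions | Adverse event or irritation question |
|---|---|---|
| Week 0 | History, examination, erythema, Q-tip test | None (baseline) |
| Weeks 1 and 3 (online) | NRS and SAL only | None |
| Weeks 2 and 4 (clinic) | History update, examination, erythema, Q-tip test, VVSQ | None |
| Week 6 (mail or online) | NRS, SAL, FSFI, VVSQ, distress scale, question on medication changes | None described |

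The VVSQ items are not reproduced in the documents, so its content cannot be checked. The plan describes it as characterising the pain and analyses it as an outcome.

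**Step 2: can the other items stand in for a question?** In part.

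- Erythema: section 4 says it may be there at entry as part of the condition. A yes/no score cannot show worsening in a woman who already has it, although a new location on the drawing can.
- Examination: it takes place at weeks 2 and 4. Irritation that clears after a woman stops, as instructed, can be gone by the visit.
- History update: it may bring irritation out, but nothing requires the question, a grade or a date.
- Tube weights: they show total use, not when or why use was interrupted.
- No text says that a finding from any of these becomes an adverse event record.

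**Step 3: illustration of size.** The only input from the plan is 32 women per arm (section 9: 64 in total, 64 / 2 = 32). The plan gives no irritation rate and no capture fraction, so there is no figure of its own to reproduce. The true rate p and captured fraction c below are assumptions.

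Expected records = 32 × p × c. Chance of no record = (1 − p × c)^32.

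| p | c | Expected records | Chance of none |
|---|---|---|---|
| 10% | 100% | 3.2 | 0.90^32 = 3% |
| 10% | 50% | 1.6 | 0.95^32 = 19% |
| 10% | 30% | 1.0 | 0.97^32 = 38% |
| 20% | 100% | 6.4 | 0.80^32 = 0.1% |
| 20% | 50% | 3.2 | 0.90^32 = 3% |
| 20% | 25% | 1.6 | 0.95^32 = 19% |

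With no events in 32, the one-sided 95% upper limit is 1 − 0.05^(1/32) = 8.9%. That limit applies to the recorded rate. At 50% capture it corresponds to a true rate of up to 8.9 / 0.5, about 18%.

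**Step 4: direction between arms.** Observed difference = c_A × p_A − c_P × p_P, where A is active and P is placebo. Take assumed true rates of 20% and 5%, a difference of 15 points:

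- 50% capture in both arms: 10 − 2.5 = 7.5 points.
- 50% on active, full on placebo: 10 − 5 = 5 points.
- Full on active, 50% on placebo: 20 − 2.5 = 17.5 points.

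Equal under-capture shrinks the difference. Unequal capture can shrink or enlarge it.

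**The case against.** The strongest case on the other side is that the plan does look at the vulva. History is reviewed at each clinic visit, the vulva and vagina are examined at weeks 2 and 4, erythema is recorded with its location and compared between arms, and the VVSQ is repeated at weeks 2, 4 and 6. A reader might infer that adverse events come to light only if women volunteer them. The documents do not support that, because these items can reveal some reactions unprompted. What they lack is a required question, a grade, and a route into an adverse event record.

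A reader might also infer that a planned tolerability conclusion will come out too favourable. The objectives, section 9 and section 12 plan no such conclusion. The synopsis phrase describes earlier practice, and the direction of any bias between arms is not fixed.

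The sentence on the main side effect concerns the 15% ointment on multiple warts three times a day, so it does not establish the main risk of this regimen. The case for asking about irritation rests instead on this plan's own instruction sheet and withdrawal rule.

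Nor are interruptions wholly unrecorded. Tubes are weighed, an irritated woman is told to notify her gynecologist, and a reduced frequency is discussed with that gynecologist. The gap is in dates and reasons.

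Finally, the rates and capture fractions above have no source in the documents, and the illustration does not separate what the visits would detect from what women would report. This stands, and is why the figures serve only to show scale.

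**Conclusion.** The point holds in a limited form. The stated method is spontaneous reporting, no described contact has a standard adverse event or irritation question, and no adverse event analysis is specified. Irritation is therefore likely to be under-counted. The amount is unknown. Under the assumed 10% rate, halving capture raises the chance of an empty record in 32 women from 3% to 19%. This rests on the visit lists and forms as the protocol describes them; case report forms and VVSQ items are not in the documents. No planned efficacy endpoint or test is affected. The change is worth making because it is cheap and the information is otherwise lost.

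**What to change.** In section 7 and in the week 2 and week 4 lists, add one scripted, non-leading adverse event question followed by one local irritation item graded none, mild, moderate or severe. Ask both identically in each arm, about the period since the last contact. Place them after the pain ratings and the Q-tip test so that they do not prime the pain scores.

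- Put the same two items on the week 1, 3 and 6 forms, also after the pain rating.
- State that new or worsened erythema compared with the baseline record is entered as an adverse event.
- Record the dates and reasons for any interruption or reduced application.
- In section 9, add a table of adverse events and of irritation by grade, by arm, with exact confidence intervals.

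The cost is two short items at contacts that already exist and one table. No visit is added and no treatment rule changes. The downside is that solicited questions will raise reported counts in both arms, so the report should say how events were sought.
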